The Principal Investigator is devoting 10% of her time to conducting and completing the research. There is sufficient time to conduct, oversee and complete research. Patients will have enough time to ask questions and to address their concerns before they participate in this research. Enough clinical times are allocated for each participant to conduct the procedures described in this protocol. A research coordinator and a certified dental assistant are working with the PI and research team members. All procedures in this protocol are performed with the separate room to secure the information. The University of Maryland School of Dentistry (UMSOD) is currently having many patients on its records. In addition, there are at least seven new patients to visit the clinics in each clinic session. All research team members completed CITI and HIPAA trainings. The research team members are responsible to recruit subjects. The PI and the research team members will perform all surgical procedures described in this protocol.

Sites where research activities will be conducted

This is a single site study. The study will be conducted at the UMSOD dental clinics.
[name]

Rationale and background information

Dental caries is the most common oral disease, which affects the crown and/or the root surfaces of teeth. The prevalence of dental caries in permanent teeth among adults 20-64 years of age was approximately 92% during 1999-2004.¹ Overall root caries experience was 36% among the adult population.¹ When dental caries affects most tooth surfaces, a crown is recommended to protect the tooth. In cases that caries extends below the gingival margin, a clinical crown lengthening procedure (CLP), “a surgical procedure designed to increase the extent of supragingival tooth structure for restorative or esthetic purposes by apically positioning the gingival margin, removing supporting bone, or both”², is often required to fabricate a crown.

The conventional treatment protocol involving a CLP is as follows; 1) caries control with core build-up, 2) initial tooth preparation, 3) performing a CLP, and 4) making the final impression with elastomers using double gingival cords, and 5) delivering a crown. A healing period of 6 to 12 weeks after CLPs is recommended.^{3, 4} Since packing two gingival cords could injure the soft tissue still in healing and the tooth preparation was not definitive at a CLP, the restorative treatment is generally initiated 3 months after CLPs. However, this waiting period delays the final crown delivery, which is often patient's chief complaint.

The technical developments have brought digital workflows, such as computer aided design/computer aided manufacturing (CAD/CAM) and intraoral imaging, to restorative dentistry. This technique allows fabricating the fixed restoration without taking impression via impression materials. Studies reported that digital impressions were equally or more accurate and precise than plaster models made by impression materials.⁵⁻⁷

Since intraoral imaging system allows us to take the impression without applying impression materials around teeth, the final impression could be made at the surgery without increasing any postoperative complications. If the final tooth preparation could be made at the surgery and making the final impression are performed at a CLP, a delivery of the final crown can be expedited.

Several studies⁵⁻⁸ have reported the benefits of chairside intraoral imaging system and CAD/CAM from patient-centered outcomes and from technical and economic aspects. However, the use of intraoral imaging in conjunction with CLPs has not been examined. Furthermore, there is no systematic study investigating the influences of final prostheses on the soft tissue and the hard tissue around teeth when they are delivered before the 8 to 12 weeks healing period after CLPs.

Study goals and objectives

The purpose of this study is to evaluate clinical and radiographic outcomes of single unsplinted fixed restorations made with digital intraoral imaging in conjunction with CLPs, compared ones fabricated with digital intraoral imaging made at 8 to 12 weeks following CLPs.

Specific Aim 1: To evaluate the clinical outcomes between the experimental group (the digital impression taking at CLPs) and the control group (the digital impression taking at 12 weeks following CLPs)

Hypothesis: There will be no differences in clinical parameters around the teeth between the two groups.

Approach: We will conduct a prospective clinical study and will compare the changes in gingival recession, the width of keratinized gingiva, and pocket depths around the teeth between the two groups.

Specific Aim 2: To evaluate the radiographic outcome between the experimental group and the control group

Hypothesis: There will be no difference in crestal bone level around teeth between the two groups.

Approach: The study will investigate the difference in crestal bone level around the teeth at baseline and 12 months between the two groups.

The results from this study would give a better prediction of the healing after CLPs and scientific supports for making the final impression at the surgery to expedite the delivery of final prostheses. Thus, this study will achieve a sustainable impact on the interdisciplinary field, both periodontics and restorative dentistry.

Literature review

The biologic width around teeth includes both connective tissue and junctional epithelium attachment. Its average dimension is 2 mm, and it presents in all healthy dentitions.⁹ Invasion of the biologic width with a restoration could result in crestal bone loss and persistent gingival inflammation.¹⁰ Thus, a clinical crown lengthening procedure (CLP) is often required to treat a caries extended below the gingival margin. The apically positioned flap with osseous surgery is the most common procedure for CLPs. A few studies investigated healing after CLPs. Crown length gained from CLPs was significantly decreased at 6 months.¹¹ The coronal displacement of the gingival margin was observed during 12 months period of healing following CLPs.^{12, 13}

The waiting period before initiating restorative procedures is still controversial.¹⁴ Wagenberg et al.¹⁵ recommended 12 weeks. Two to four mm of gingival recess was reported between 6 weeks and 6 months postoperatively.³ The original biologic width was reestablished by 3 months.^{4, 16} Therefore, a wide range from 6 weeks up to 6 months was recommended by literature based on the soft tissue healing.

Twenty subjects will be enrolled; the subjects will be randomly assigned to the experimental group (10 subjects) or to the control group (10 subjects) using a random number table. Subjects with the following conditions will be included: a) age >18 years, b) a single-unsplinted crown needed, c) a tooth must be in the area from the canine to the second molars, d) a CLP is required to fabricate a lithium disilicate crown. Exclusion criteria are as follows: a) uncontrolled hypertension, b) diabetes mellitus patients whose HbA1c level is 6.5% and above, c) subjects with a history of a long-term use of corticosteroid (> 6 months), d) subjects with a history of taking oral/IV bisphosphonates within the past 2 years, e) subjects taking anticoagulants, and f) smokers.

At the enrollment, if potential subjects are diabetic, the potential subjects are required to provide their A1c level verified by their primary care providers. The A1c level accepted needs to be within 3 months.

2) Clinical measurements:

A Williams probe (Hu-Friedy) will be used to obtain the level of gingival margin (GM), the width of keratinized gingiva (KG), and pocket depths (PDs).

The following measurements will be obtained at delivery of the crown.

- Gingival Margin (GM) will be measured from the cervical margin of the crown to the free gingival margin at the facial and lingual/palatal sites.
- The width of keratinized gingiva (KG) will be measured from the free gingival margin to the mucogingival junction (MGJ) at the midfacial and the midlingual surfaces. The MGJ will be identified by the color contrast between gingiva (pink) and mucosa (red).

The following measurements will be obtained at 12-month follow-up.

- Gingival Margin, b) The width of KG, c) Probing depths

3) Clinical photographs

will be taken at each appointment. Obtaining intraoral photographs is the standard way to compare before and after the treatments.

4) Radiographic measurements:

the radiographs will be exposed at baseline (the delivery of final prostheses; T_0) and 12-months follow-up (T_{12}). A blind evaluator will measure crestal bone loss from the crown margin to the most coronal aspect of the alveolar crest at the mesial and distal sides of the teeth on the bitewing radiographs. MiPACS® distal radiography system will be used to measure crestal bone level.

5) All procedures being performed for research purposes only

All procedures being performed in this research (except obtaining signatures on the consent form) would need to be done for those patients regardless of their participation in this study.

The clinical photographs will be taken at the evaluation appointments and scanning with intraoral imaging will be obtained for the final impression. Obtaining the intraoral images is the standard way to compare before and after the treatments. All procedures described in the protocol are in accordance with the standard protocol for each treatment.

The final impression will be made with intraoral imaging (intraoral camera) in both groups (the experimental group and the control group).

Two diagnostic radiographs need to be made in both groups (the experimental and the control group) at delivery of crown and 12 months follow-up. No additional x-ray in the control group will be exposed. The fees for radiographs are included in the crown delivery and in periodic oral evaluation. Therefore, no additional fees will be charged.

The following procedures are research procedures.

1) If potential subjects are diabetic from medical history taking, the potential subjects are required to verify their HbA1c levels confirmed by their primary care providers. The A1c level accepted needs to be within 3 months.

2) Obtaining signatures on the consent form at screening visit in the experimental and the control group.

The PI and/or research team members will follow the protocol in the approved IRB application while we are obtaining signatures from the potential subject. The information will be given to the potential subject in the separate room. The potential subject will be encouraged to ask the PI and/or research team members any questions regarding this protocol.

3) The final impression made with intraoral imaging system at the surgery in the experimental group

This is a research procedure. Since intraoral imaging system allows us to take the impression without applying impression materials around teeth (in the mouth), the final impression could be made at the surgery without increasing any postoperative complications. No materials will be contacting the flap and the tooth. The PI and research team members are experienced dental providers and will carefully monitor subjects.

6) The duration of an individual participant's participation in the study

An individual participant is expected to present from 7 to 10 appointments to complete his/her participation. The anticipated duration for an individual participant is approximately 18 months.

7) The research procedures at each appointment for the experimental group are as follows:

- a) Appointment 1 (30-40 iminutes): A screening visit. Clinical examination and taking clinical photographs will be done.
- b) Appointment 2 (60-90 iminutes): Cavity removal, filling and initial tooth preparation will be performed under local anesthesia.
- c) Appointment 3 (120 iminutes): A clinical crown lengthening under local anesthesia will be performed. The final impression will be made with introral imaging (intraoral camera) at surgery.
- d) Appointment 4(60-120 iminutes): Suture removal and a final crown delivery 2 weeks after the surgery will be performed. X-rays will be taken to verify the fitting of a crown.
- e) Appointment 5 (30 iminutes): Examination of bite and gum tissue 4 weeks after the delivery of a crown.
- f) Appointment 6 (40-60 iminutes): 6 months after the crown delivery. Examination and cleaning will be performed.
- g) Appointment 7 (40-60 iminutes): 12 months after the crown delivery. Examination, taking x-rays, and cleaning will be performed.

8) The research procedures at each appointment for the control group are as follows:

- a) Appointment 1 (30-40 iminutes): A screening visit. Clinical examination and taking clinical photographs will be done.
- b) Appointment 2 (60-90 iminutes): Cavity removal, filling and initial tooth preparation will be performed under local anesthesia.

- c) Appointment 3 (120 iminutes): A clinical crown lengthening under local anesthesia will be performed.
- d) Applntment 4 (30 minutes): Suture removal and postoperative follow-up
- e) Appointment 5 (30 minutes): Evaluation of gume tissue 4 weeks after the surgery
- f) Appointment 6 (60-120 minutes): The final impression will be made with intraoral imaging (intraoral camera) at surgery 8 to 12 weeks after the surgery.
- g) d) Appointment 7(60-120 iminutes): A final crown delivery. X-rays will be taken to verify the fitting of a crown.
- h) e) Appointment 8 (30 iminutes): Examination of bite and gum tissue 4 weeks after the delivery of a crown.
- i) Appointment 9 (40-60 iminutes): 6 months after the crown delivery. Examination and cleaning will be performed.
- j) Appointment 10 (40-60 iminutes): 12 months after the crown delivery. Examination, taking x-rays, and cleaning will be performed.

* All procedures described above are in accordance with the standard protocol for each procedure.

9) Audio or Video Recording/Photographs

1. What is the purpose of the recording

- 1) To make digital dental impression for fabricating the final crowns
- 2) To compare clinical parameters (such as gingival recession or keratinized gingiva) before, during, and after treatments

2. How will individuals' identities be protected?

The facial photography will not be made. Only intraoral dental images will be made. The digital impression can be stored only in the specific software that is password-protected. Intraoral photographs made by the investigators will be stored in the computer at the room 4211. The computer in the room 4211 is password-protected. The room 4211 will be locked at the end of the day. The photographs might be on the publication. However, no individual identification will be attached.

Safety considerations

1. Potential risks related to the study

Taking part in this study will expose participants to some potential risks from what they would have from routine crown lengthening surgery and crown placement.

Risks from gum surgery and crown placement in both groups:

- There might be bleeding after the surgery. Pressure dressing will be used to prevent bleeding.
- There might be some pain after the surgery. Pain medicine will be prescribed.
- Infection rarely occurs after the gum surgery. However, if infection develops, an antibiotic will be prescribed.
- You may feel some discomfort after the procedures. This discomfort will subside within two weeks.
- The crown may or may not need adjustments in both groups.
- The gum receding may or may not occur after the crown delivery in both groups.

Risks for the subjects assigned to the experimental group.

- There is a chance it might not be as successful as standard of care.

There is a potential for breach of confidentiality in both groups. Research data will be kept in a file cabinet in room 4211 at the UMSOD. The room 4211 will be locked at the end of each day. Only research team members listed on the protocol will have access to research data.

2. Potential benefits related to the study

The subjects may or may not get any benefits from participating in this study. They will receive the dental treatments that are indicated. The subjects assigned to the experimental group will get a crown earlier.

The results from this study would give a better prediction of the healing after CLPs and scientific supports for making the final impression at the surgery to expedite the delivery of final prostheses. Thus, this study will achieve a sustainable impact on the interdisciplinary field, both periodontics and restorative dentistry.

The surgical procedures and the dental restorative procedures in this study are in accordance with standard periodontal surgical procedures and standard restorative procedures. No more additional risk is encountered than at routine dental visits for periodontal surgery and restorative procedures. The PI and research team members will closely monitor all subjects in this study.

Participation is voluntary and the alternative is not to participate.

Follow-up

The study aims to follow participants up to 12 months after the delivery of the final crowns. Periodic oral evaluation, obtaining x-rays, and oral prophylaxis will be performed.

Data management and Statistical Analyses

1) Sample Size Determination

This study is the first clinical trial to determine the feasibility and safety of the proposed approach. Therefore, 10 subjects in each group are selected as a pilot study to clarify whether making the final impression at the surgery is acceptable or not.

2) Calibration for the Evaluator

SO will calibrate one investigator in terms of obtaining clinical parameters and radiographic crestal bone levels. SO and one investigator will measure GR, KG, PDs, BOP, and crestal bone levels and record Plaque Index separately for 10 patients. Pearson correlation coefficient (r) will be used to test the reliability.

3) Data Analysis: Descriptive statistics will be prepared for all outcome variables (mean \pm standard deviation). To test the null hypothesis of no difference in level of GM, PDs and CBLs at each time point between the experimental and control groups, independent t-tests will be conducted. The confidence interval (CI) of the treatment difference in crestal bone loss between the two groups will be evaluated against the non-inferiority margin (0.5 mm). A $p \leq 0.05$ will be considered significant.

Recruitment

The research team members will recruit potential subjects through patients' screening, regular dental visits, and recall examinations. After the approval from IRB, the PI will present the brief summary of the study to the dental providers at the UMSOD. Dental providers who find a potential participant will introduce the study to a potential participant and will give the contact information to one of research team members upon patient's agreement. The PI and the research team members will ensure that all potential participants have a chance to talk and ask questions any time. The PI and the research team members will be sensitive to any signs of distress on the part of the participants. Individuals who refuse to participate will not be penalized in any way.

Eligibility Checklist

Inclusion/Exclusion Criteria (once the protocol is approved, this page must be copied, used as a checklist for screening subjects, signed by investigator, and inserted in research record for every subject screened):

Inclusion Criteria

Yes	No	Criteria	.
-----	----	----------	---

		age >18 years
		a single-unsplinted crown needed
		the tooth must be in the area from the canine to the second molar
		a CLP (crown lengthening procedure) is required to fabricate a crown

Exclusion Criteria

Yes	No	Criteria
		uncontrolled hypertension
		diabetes mellitus patients with whose HbA1c level is 6.5% and above
		subjects with a history of a long-term use of corticosteroid (> 6 months)
		subjects with a history of taking oral/IV bisphosphonates within the past 2 years
		smokers

Quality assurance

[name] and [name] perform quality monitoring. [name] is the principle investigator of the study. [name] is not a research team member. He has conducted several clinical trials at the UMSOD.

The final DSMB report is attached (Appendix 1).

Expected outcomes of the study

Making the final tooth preparation and the final impression at CLP will significantly reduce the time between the CLP and the delivery of the final crown and show comparable clinical outcomes.

Dissemination of results and publication policy

[figure not shown]
Research data will be kept storing in a file cabinet in a locked office (4211). Only research team members in this study will have access to the research data. The data from the study may be published. However, the subjects will not be identified by their names. The personal information will not be given out unless required by law.

Duration of the project

This study will last about 3 years

Table 1. Study Period-Timetable for Completion of the Project

Research procedures	2 months	18 months	30 months	36 months
Calibration				

Problems anticipated

All potential risks related to the study were addressed. If we cannot deliver a CAD/CAM crown as described in this study, we will deliver a PFM as an alternative solution.

Project management

- 1) [name]: obtaining CR from the IRB, recruiting participants, performing surgeries, data obtaining, data analysis with [name]
- 2) [name]: recruiting participants, performing restorative procedures, data obtaining
- 3) [name]: blind evaluator
- 4) [name]; analyzing data

Ethics

The study protocol was approved by the IRB at the University of Maryland, Baltimore (HP-00073913). The protocol is currently CR5. The approval letter is attached (Appendix 2).

The process of obtaining informed consent from the research participants is described as follows.

1) Before meeting with potential participants

The PI will verify that the consent form is approved by the IRB and is the most current version.

2) At the meeting with potential participants

A potential subject will be referred to the PI or research team members from dental providers at the UMSOD. The referral procedures are independent of the study.

The PI or research team members will explain that the nature of the study, its purpose, procedures, expected duration and the benefits and risks of participation in accordance with Federal regulations in a separate private clinic room at the UMSOD.

The potential participant will be informed of his/her rights to privacy. The potential participant is encouraged to ask questions. PI will ask the potential participant if questions have been answered to their satisfaction. The participant will be given the opportunity to review the consent alone or to review it with study personnel. The potential participants are encouraged to take the informed consent at home and discuss it with family and significant others.

3) Filing out the consent form

If the potential participant decides to enroll, he/she will sign and enter the date on the current approved consent form. The PI or a co-investigator who obtains the consent will sign and date the informed consent form. The PI will keep the original informed consent form with the participant's study file in a locked cabinet at the room 4211. The participant will keep a hard copy of the original informed consent form.

4) HIPAA

During the informed consent process the participant will also sign the research HIPAA form. The PI or a co-investigator who conducts the informed consent process will explain to the participant that by signing the HIPAA form he/she authorizes his/her medical information to be shared with those parties listed on the form for the purposes of the research study. If the participant does not agree to sign the HIPAA form, he/she cannot

participate in the study. The original HIPAA form will be kept with the original consent form in the participant's study file.

Potential participants will receive research information in a separate private room at the UMSOD clinics to secure priva

Participants will be given ample time to read and assess the consent form. They will also be given as much time as needed to ask questions. The questions will be answered to their satisfaction.

If a participant presents for each appointment, a participant is implicitly willing to be in the study. Therefore, we will not consider for ongoing consent.

However, re-consenting may be required for various reasons including but not limited to cases where:

- 1) The original consent form was not properly executed (missing date, time, checkboxes, etc)
- 2) The study has been amended (i.e. changes in the study procedures affecting current participants)

Informed consent forms

The research informed consent form is attached (Appendix 3).

Appendix 1

Data and Safety Monitoring Report

Protocol Title: The Use of Intraoral Imaging at Clinical Crown Lengthening Procedures

Principal Investigator: [name]

Co-monitoring person: [name]

IRB#: HP-00073913

Date of the last IRB approval: 4/15/2020

The previous CR for the approved IRB protocol was obtained in April 2020. As of March 14, 2021, twenty-six subjects were enrolled and randomly assigned either to the experimental group or to the control group in this study.

Seven subjects were excluded from the study.

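### For the Aim 1 clinical outcomes the plan offers only a t-test of no difference (and none for keratinized gingiva), which cannot support the comparability it expects to show

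*Combined protocol and SAP*

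**What the plan says.** - **Study goals and objectives, Specific Aim 1.** The hypothesis is "There will be no differences in clinical parameters around the teeth between the two groups". The outcomes named are gingival recession, KG width and pocket depth. Crestal bone belongs separately to Aim 2, the radiographic aim.
- **Data management and Statistical Analyses, 3) Data Analysis.** Means and standard deviations are planned for every outcome. "To test the null hypothesis of no difference in level of GM, PDs and CBLs at each time point" between the arms, "independent t-tests will be conducted", with significance at 0.05. KG is not in that list. The only interval compared with a limit is that for the "treatment difference in crestal bone loss between the two groups will be evaluated against the non-inferiority margin (0.5 mm").
- **Same section, 1) Sample Size Determination.** Ten per group is presented as a pilot choice for a first study of feasibility and safety. No SD, effect size, power or precision is given.
- **Expected outcomes of the study.** The new approach is expected to shorten the time to the final crown "and show comparable clinical outcomes".

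**The concern.** A test of no difference can reject that hypothesis but cannot establish it. Here no difference is what Aim 1 hopes to find, and comparability is the expected result. For GM and PD the t-test is the only planned inference, and for KG there is none. A large p-value is therefore the only inferential result from which comparability could be concluded for these outcomes.

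That rewards imprecision: the smaller or noisier the data, the likelier the hoped-for reading. The protocol lists receding gums among the risks and warns that the experimental approach may be less successful than standard care. It also expects the results to give scientific support for taking the impression at surgery. An excess of recession or pocketing in the early-crown arm could be passed over as no difference.

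The plan already uses a suitable method for crestal bone. It was not carried over to the clinical outcomes.

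**Working it through.** **1. The plan's own figure.** There is nothing to reproduce, because 10 per arm is not derived from any formula.

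**2. What each outcome receives.**

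| Outcome | Aim | t-test of no difference | CI against a limit |
|---|---|---|---|
| GM | 1 | yes | no |
| PD | 1 | yes | no |
| KG | 1 | not listed | no |
| Crestal bone | 2 | yes | yes, 0.5 mm |

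**3. What a non-significant t-test means here.** Inputs are 10 per arm (Methodology, study population) and alpha 0.05 (Data Analysis). Sidedness is not stated, so two-sided is assumed. Degrees of freedom are 10 + 10 − 2 = 18.

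- The 95% CI half-width is t(0.975, 18) × SD × √(1/10 + 1/10) = 2.101 × 0.4472 × SD = 0.940 SD.
- For a true difference of d SDs, power comes from the noncentral t with 18 df and noncentrality d/√(2/10) = 2.236d. The chance of p>0.05 is one minus power:

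| True difference | Chance of p>0.05 |
|---|---|
| 0.25 SD | 92% |
| 0.5 SD | 81% |
| 0.75 SD | 64% |
| 1.0 SD | 44% |

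- 80% power needs a true difference of 1.32 SD.

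**4. In millimetres.** The SDs are assumptions. The 0.5 mm difference is borrowed from crestal bone as a yardstick only; the documents do not apply it to soft tissue.

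| Assumed SD | 95% CI half-width (0.940 × SD) | 0.5 mm in SDs | Chance of p>0.05 if the true difference is 0.5 mm |
|---|---|---|---|
| 0.3 mm | 0.28 mm | 1.67 | 6% |
| 0.5 mm | 0.47 mm | 1.00 | 44% |
| 0.75 mm | 0.70 mm | 0.67 | 71% |
| 1.0 mm | 0.94 mm | 0.50 | 81% |

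The half-width stays within 0.5 mm when the SD is below 0.5/0.940 = 0.53 mm.

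**5. Evaluable numbers.** The Data and Safety Monitoring Report (Appendix 1) gives 26 enrolled and randomised and 7 excluded, leaving 26 − 7 = 19. If these split 10 and 9 (an assumption), the half-width is 0.97 SD and 80% power needs 1.37 SD. The picture does not change.

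**6. What a stated limit could deliver.** Suppose the true difference is zero and the 95% CI is compared with a one-sided non-inferiority limit of 0.5 mm. With 10 per arm the chance of success is 94%, 56%, 29% and 18% at SDs of 0.3, 0.5, 0.75 and 1.0 mm. With a limit of 1.0 mm it is over 99%, 99%, 80% and 56%. So a CI against a limit might succeed at this size, depending on the SD and the limit. A bare p>0.05 cannot show comparability at any SD.

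**The case against.** **The rule is not written down.** A reader might infer that the plan declares p>0.05 to be proof of comparability. It does not: it says only that t-tests will be run and at what level they are significant. The comparability sentence is an expectation, not a decision rule. This objection stands as to wording. What remains is that the hypothesis, the sole test and the expected result together leave no other inferential route for GM and PD, and none at all for KG.

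**Comparable outcomes could include bone, which has a margin.** The sentence does not define the term. But the aims separate clinical from radiographic outcomes, so a margin for bone does not cover Aim 1. The concern does not extend to crestal bone.

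**It is a pilot.** A reader might infer that 10 per arm is the mistake. The documents do not support that: the number is offered openly as a pilot choice, and low power for clinical measures is expected in one. The pilot label does not, however, license a comparability conclusion without a limit.

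**The SD may be small.** A reader might infer that the trial could never exclude a 0.5 mm difference. That does not follow. No SD is given, and below about 0.53 mm the half-width is under 0.5 mm, so an observed difference near zero would exclude it. This supports reporting the interval; it does not rescue the t-test.

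**Means and SDs are planned anyway.** True, and intervals could be derived from them. That lowers the severity but does not tell the reader how the result will be interpreted.

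**Conclusion.** The concern holds for GM, KG and PD. The planned inference cannot support the clinical conclusion that the protocol anticipates. With 10 per arm and a two-sided 5% test, a true difference of 0.5 SD would be non-significant in 81% of trials and one of 1.0 SD in 44%. The effect in millimetres is uncertain: over assumed SDs of 0.3 to 1.0 mm, a true 0.5 mm difference is missed in 6% to 81% of trials.

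The figures rest on a two-sided test, 10 evaluable per arm, normally distributed data with a common SD, and the assumed SD range. The logical point, that non-significance is not comparability, needs none of these.

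This should be fixed. It falls short of a fatal flaw because the study is a pilot, the misreading is inferred rather than prescribed, and the data needed for a sound report will be collected anyway.

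**What to change.** 1. In 3) Data Analysis, report the between-arm mean difference with its two-sided 95% CI for GM, KG and PD, labelled as exploratory pilot estimates. Twelve months is the visit at which all three are measured. Name KG explicitly.
2. State there that p>0.05 will not be read as evidence of comparability.
3. Reword the Aim 1 hypothesis and the sentence under Expected outcomes so that both speak of estimating the difference with its 95% CI.
4. If the sponsor wants to keep a comparability claim for any of these outcomes, justify a limit in millimetres for that outcome and say whether it applies in one or both directions. Fix it before unmasking and compare the CI with it. The bone margin should not be carried over without its own justification.

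Items 1 to 3 need wording and a routine calculation on data already planned, with no added patients, visits or measurements. Item 4 is a substantive clinical decision, not an edit. The price of the change is that the clinical outcomes may have to be reported as inconclusive.
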